A Pragmatic Trial of Brief CBT for Anxiety in VA Primary Care

Funding Agency: Office of Research and Development

Principal Investigator/Study Chair: [name]., and [name].

IIR 18-233 CIRB 20-22 NCT04523779

Version 9: March 20, 2023

Abstract

Anxiety disorders are common in VA primary care settings and are associated with substantial functional impairment, poor health-related quality of life, suicide, and high rates of comorbid psychiatric and medical disorders. No brief psychotherapy interventions for anxiety currently exist for VA primary care settings - where many Veterans seek care. Cognitive Behavioral Therapy (CBT) is a first line treatment for anxiety but Primary Care Mental Health Integration (PCMHI) providers need an intervention approach for anxiety disorders that is brief, problem-focused, and fits into their system of care.

This 4-year, multisite trial will use a pragmatic randomized trial design to examine the effectiveness and implementation potential of a brief CBT intervention for anxiety delivered either in-person or via VA Video Connect-Home, according to patient preference. CBT will be delivered by existing PCMHI providers at three large VAMCs. Aim 1 will examine the clinical effectiveness of the bCBT intervention vs. EUC for anxiety and quality of life at 4-, 8-, and 12-month follow-ups. Aim 2 will determine factors associated with bCBT response and explore Veteran demographic and clinical factors associated with VVC-H engagement. An exploratory aim will use mixed, qualitative and quantitative methods to better understand implementation successes and challenges related to delivery and impact of bCBT anxiety and VVC-H use in the PCMHI setting.

The project will embed bCBT into PCMHI programs using existing VHA providers. A total of 225 Veterans diagnosed with an anxiety disorder will be recruited from three VAMCs. Eligible Veteran participants will be randomized to a bCBT or to an Enhanced Usual Care (EUC) condition. A professionally diverse set of PCMHI providers will be invited to deliver bCBT. Providers will receive bCBT training and support to embed treatment into their existing practice setting. Veterans randomized to bCBT will receive 4 – 9 sessions based upon treatment response (50% reduction in GAD-7) by session 4. Veterans will also be offered the choice of receiving bCBT in-person or through VVC-H. EUC participants will receive 4 brief monthly check-in calls from study staff and a note placed in their medical record alerting their provider to the presence of significant anxiety symptoms. BCBT treatment and EUC check-in calls will end at 4 months.

The project leverages VA stakeholders at all levels to improve alignment of the work with VA and Veteran initiatives. Clinical outcomes will provide justifications or cautions to inform future evidence-based psychotherapy (EBP) programs. If positive, data will be used to assist VA leadership in the expansion of EBPs and VVC-H in PCMHI. For example, should the project produce robust clinical outcomes - next steps would involve a non-research / demonstration project in one or two VISNs where the project team will train and support a wider group of providers in the delivery of brief CBT for anxiety. The project team will use the training program and clinical intervention materials as well as lessons learned from the proposed HSR&D IIR to support and enhance brief CBT delivery in a non-research context.

List of Abbreviations

Provide a list of all abbreviations used in the protocol and their associated meanings.

ACOS – Associate Chief of Staff
AUDIT-C – Alcohol Use Disorders Identification Test
bCBT – Brief Cognitive Behavioral Therapy
CAPRI – Compensation and Pension Record Interchange
CBT – Cognitive Behavioral Therapy
CCI – Charlson Comorbidity Index
CoE – Center of Excellence
Co I – Co-Investigator
CPRS – Computerized Patient Record System
DSM-5 – Diagnostic and Statistical Manual of Mental Disorders version 5
DSMB – Data Safety Monitoring Board
EBP – Evidence Based Practice
ERS – Expectancy Rating Scale
EUC – Enhanced Usual Care
FE – Formative Evaluation
GAD – Generalized Anxiety Disorder
GAD-7 – General Anxiety Disorder (7-item scale)

2.0 Introduction

- Provide scientific background and rationale for study.
- Include summary of gaps in current knowledge, relevant data, and how the study will add to existing knowledge.

Anxiety disorders are common in VHA primary care and PCMHI settings, but standardized, evidence-based treatment practices for use in these settings are lacking. In FY2017, 657,194 Veterans enrolled in the VHA were diagnosed with an anxiety disorder. Anxiety disorders are associated with substantial functional impairment, poor

health-related quality of life, suicide, and high rates of comorbid psychiatric and medical disorders. Patients with anxiety symptoms are most likely to present in primary care settings, yet rates of treatment are low. In contrast to the advances in treatment of depression and PTSD in VHA, far less attention has been paid to anxiety disorders, despite their high prevalence and associated impairment. For instance, the VHA developed specific practice guidelines for depressive disorders and posttraumatic stress disorder (PTSD), but such guidelines are not available for anxiety disorders. At the same time, the VHA Uniform Mental Health Services handbook requires that Veterans with anxiety disorders have access to EBPs, yet no EBPs for anxiety disorders appropriate for the PCMHI setting have been disseminated. PCMHI providers, who must deliver brief treatments, are left to adapt high intensity EBPs, potentially decreasing the potency of efficacious treatments.

Cognitive behavioral therapy (CBT) is an EBP for all types of anxiety disorders including generalized anxiety disorder (GAD), panic disorder, and social anxiety disorder. However, CBT must be tailored to fit the PCMHI setting, as traditional CBT anxiety interventions were developed for specialty mental health settings, often target specific anxiety diagnoses, and typically require 12-16 sessions of therapy. This intensive model of care is incongruent with the brief intervention approach required for VHA's PCMHI model. Further complicating delivery of CBT for anxiety disorders in PCMHI, repeated exposure to feared cues is considered a critical component of CBT for anxiety but is rarely used in PCMHI and primary care settings¹. In the absence of EBPs for anxiety tailored to the PCMHI setting, data suggest that most psychotherapy being delivered in PCMHI settings is supportive in nature and not evidence-based care.²

Our proposed bCBT treatment for anxiety was specifically designed for use within VA PCMHI settings and uses a patient-centered approach to increase engagement while addressing the mental health needs of anxious Veterans. Emphasis was placed on maximizing intervention potency and minimizing intensity and duration to improve implementation value and alignment with VA PCMHI requirements. The intervention directly addresses challenges to delivery of CBT providing 1) a brief, practical model of care to address multiple anxiety conditions consistent with the PCMHI model (e.g. 4-6 sessions; measurement-based care), and 2) a clinically potent intervention that includes exposure-based skills.

The project also seeks to better understand how Veterans and providers can use VVC-H to improve access to and engagement with EBPs. Video-delivered psychotherapy is as effective as in-person delivery with comparable rates of patient satisfaction³. Furthermore, VVC-H delivery has the potential to increase access to care for Veterans facing barriers to in-person care and may improve the efficiency of care in VHA as PCMHI resources are accessed virtually, freeing up costly space at the hospital and freeing hospital support staff to focus on other tasks. Consistent with VHA priorities to modernize the healthcare system and increase access to care, Veterans should be

offered the choice of receiving PCMH services via telehealth or in-person whenever possible. Although VHA is pioneering implementation of VVC-H technology in specialty mental health clinics, its use in PCMH settings is rare, and fewer than 1% of Veterans have received mental health care via VVC-H. The current proposal seeks to better understand provider and Veteran attitudes and experiences with VVC-H services to inform future efforts to expand utilization of VVC-H throughout VHA.

The proposed research directly responds to the VHA and HSR&D priority areas of access to care and telehealth and uses a pragmatic trial design and implementation science to support ORD's priority goals of increasing Veterans' access to high quality clinical trials and increasing the real-world impact of research.

3.0 Objectives

- Describe the study's purpose, specific aims, or objectives.
- State the hypotheses to be tested.
- Indicate the relevance to Veterans and the VA

The primary hypothesis is that anxiety outcomes, as measured by the GAD-7, and quality of life, measured by the SF-12 will be superior at 4-, 8-, and 12-month follow up for patients who are assigned to receive bCBT vs. EUC.

Primary Aim: To determine whether anxiety symptoms (GAD-7) and quality of life (SF-12) differ as a function of the intervention (bCBT for anxiety vs. EUC) at 4-, 8-, and 12-month follow-ups.

Secondary Aims: (Prediction of bCBT response and VVC-H use (bCBT group only)): A) To identify factors associated with bCBT response, namely whether bCBT is effective for specific anxiety disorders (e.g. generalized anxiety, panic, social phobia) and whether number of sessions received, and treatment engagement are critical to outcomes. B) To identify Veteran demographic and clinical factors associated with VVC-H use.

Exploratory Aims: A mixed-methods formative evaluation, informed by RE-AIM QuEST, will collect data related to Reach (#of Veterans receiving bCBT and VVC-H), Effectiveness (bCBT and VVC-H impact), Adoption (# of providers using bCBT and VVC-H), and Implementation (provider bCBT program fidelity and VVC-H potential). Data will be collected from qualitative interviews with Veterans and providers and integrated with quantitative data from provider surveys and chart reviews of bCBT and VVC-H use. With the ORD supplement to the main project, [name] will leverage the diverse Veteran populations included in the multisite

parent study (Houston, San Antonio, and New Orleans VA MCs) to understand barriers to treatment and research access for African American and Hispanic Veterans.

The relevance of the research to Veterans is that it will help improve access to mental health services for anxiety problems. The integration of mental health services into primary care has increased access to treatment, but Veterans recently diagnosed with anxiety disorders are still less likely to receive any or as much treatment as other Veterans diagnosed with problems like depression or PTSD. Therefore, effective and time-limited interventions suitable for primary care are needed for this population. In addition, delivering mental health services in a way that matches Veteran preferences and reduces barriers to receiving treatment will further reduce this service gap. The knowledge this project is likely to generate will directly address VHA strategic goals related to improved access to high quality mental health care and increased availability and use of telehealth services (e.g. VA Video Connect-Home; VVC-H).

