5.0 Study Procedures

5.1 Study Design

- Describe experimental design of the study. Include sequential and/or parallel phases of the study, including durations, and delineate which interventions are standard of care and which are research.
- Include a description of how anticipated risk will be minimized and include an analysis of risk vs. potential benefit.

- Provide description of the study population (delineate all categories of subjects – patients, providers, family members, employees, etc.). Include anticipated enrollment numbers
- Include rationale for including or excluding certain populations – in particular vulnerable populations.
- As applicable, provide information on any added protections for vulnerable populations.
- If applicable include information on data and/or specimen banking to include where the bank is located, who will own the data and/or specimens, and who is overseeing the repository.

The proposed 4-year, multisite, randomized pragmatic trial will assess the real-world application of bCBT for Veterans with anxiety, as delivered by frontline VA PCMHI providers at three facilities (Houston, San Antonio, and New Orleans). Veteran participants will be randomized to bCBT or to Enhanced Usual Care (EUC). EUC participants will receive anxiety education materials, a note in their medical record indicating the presence of elevated anxiety symptoms, and 4 brief monthly check-in calls with project staff. Participants randomized to bCBT will have the option to receive bCBT for anxiety delivered either in person, via VVC-H, or both. The primary outcome, anxiety symptoms, will be evaluated at 4-, 8- and 12-month follow-ups.

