5.5 Study Evaluations

- Describe all evaluations to be conducted (including screening; tests/questionnaires that will be administered; any procedures that

subjects will be required to complete) and data collection methods. Include materials as an appendix or separate attachment.

Aims 1 & 2 Quantitative Measures: Measures were selected for their strong psychometric properties, ability to detect patient-centered change, and feasibility for adoption/implementation within VA PCMHI clinics.

Anxiety: We chose the Generalized Anxiety Disorder Screener (GAD-7¹⁴) as our primary anxiety measure because of its brevity, psychometrics and, most importantly, because it has been adopted by VHA's national PCMHI program. The GAD-7 is a seven-item self-report instrument that is psychometrically strong and valid for use in the primary care setting^{5,14}. A GAD-7 score of 10 or higher will be required for study inclusion. Treatment response will be defined as a 50% reduction in baseline GAD-7 scores. Note: Study staff will administer the GAD-7 as part of all outcome assessments; bCBT providers will also administer it as part of their MBC practices when delivering bCBT.

The Overall Anxiety Severity and Impairment Scale (OASIS¹⁵) will be a secondary measure of anxiety. Unlike the GAD-7, which will be administered by both research staff and PCMHI providers, the OASIS will only be administered by research staff, thereby avoiding response bias that may occur in the clinical setting. The OASIS is a widely used five-item measure of anxiety for primary care settings^{5,16} assessing anxiety frequency, anxiety severity, avoidance behaviors, social interference, and interference at work, school, or home¹⁵. The OASIS has demonstrated good internal consistency, and convergent and divergent discriminative validity in primary care^{16,17}. A 50% reduction in symptoms on the OASIS is indicative of treatment response^{5,6}.

Quality of Life and Functional Status: We will assess quality of life using the 12-item Short Form Health Survey for Veterans (SF-12V¹⁸), an instrument adopted by VHA as a measure of functional status. SF-12V responses can be summarized in component scores for physical (PCS) and mental (MCS) functioning. Minimally clinically important differences (MCIDs) for PCS and MCS scores are a change of 5.0 or more^{19,20}.

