Analyses will use data from the mixed-method formative evaluation described above. Qualitative pre-implementation data will be analyzed using rapid qualitative analysis, a systematic and rigorous process, to provide data in real-time to tailor the intervention, and identify contextual barriers prior to rollout^{38,39,40}. Implementation and post-implementation interviews with providers and Veterans will be analyzed using directed content analysis⁴¹ consisting of deductive (a priori) codes from the RE-AIM QuEST framework. Inductive (a posteriori) codes that emerge from providers' and Veterans' experiences with the intervention and VVC-H delivery will also be identified. We will utilize Atlas.ti software to facilitate analysis and management of qualitative data. Quantitative data will be collected and analyzed as descriptive data.

Sample Size and Power Calculations

Primary Aim: To determine whether anxiety symptoms (GAD-7) and quality of life (SF-12) differ as a function of the intervention (bCBT for anxiety vs. EUC) at 4-, 8-, and 12-month follow-ups. A three-step sample-size calculation indicates that 225 anxiety patients will need to be randomized to draw conclusions regarding the primary hypothesis that bCBT will be superior to EUC at 4-, 8, and 12-month assessments.

Step 1: Power to detect GAD-7 differences. A sample size of 138 anxiety patients is needed to detect an effect size = 0.38 for the differences between bCBT and EUC GAD-7 outcomes using a two-sided t-test with 80% power at the .05 significance level, adjusted for repeated measures³⁷. The formula for the sample size, adjusting for repeated measures, is

$$N = \frac{2 * (Z_{(1-\alpha/2)} + Z_{(1-\beta)})^2 [1 + (T - 1) \rho]}{d^2 T}, \text{ where } N \text{ is the sample size per group, } Z_{(1-\alpha/2)} \text{ and}$$

$Z_{(1-\beta)}$ are the $(1-\alpha/2)$ and $(1-\beta)$ percentiles of the normal distribution, T is the number of follow-up measures, ρ is the correlation coefficient of the repeated measurements, and d is the effect size⁴². Solving this with $T = \text{three follow-up measurements after baseline}$, $d = 0.38$, and $\rho = .7$ yields a sample size per group of 69, and total sample $N^t = 138$.

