## DATA ANALYSIS PLAN

### Primary aim: Anxiety and Quality of Life differ as a function of bCBT for anxiety vs. EUC

All analyses will be done on an intention-to-treat basis, and participants will be analyzed in the group to which they were randomized. We will first determine whether participants randomized to the two study arms differed on baseline characteristics, age, race, gender, medical or mental health comorbidities, and anxiety. Chi-square tests will be used for categorical variables and t-test for continuous and ordinal variables.

We will examine the normality of the distributions of both primary outcomes and will consider transformations such as the log or the inverse. Because we are using an unequal randomization (see sample size section), it is especially important to test the assumption about the homogeneity of the variance of the residuals across the levels of the independent variables. For analyses of our primary outcomes, we will test the homogeneity assumption before testing for differences between the bCBT and EUC groups. If the assumption of equal variances is violated, we will use statistical tests such as the approximate t-test, which uses individual sample variances instead of the pooled variance. In addition, we will obtain Satterthwaite's approximation of the degrees of freedom. For the regression models, we will test whether the residual variances are equal and, if necessary, we will fit unequal variance models to obtain better estimates of the standard errors of the difference between groups. We will calculate the absolute differences in outcome measures between baseline and 12-month follow-up and the effect sizes of the bCBT group compared with EUC. We will also examine effect sizes for the bCBT group baseline vs. post-treatment and 8-month follow-up.

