To compare changes in anxiety symptoms between the two groups over time, we will use a longitudinal, mixed-model analysis containing terms for the intercept, treatment, time, and interaction between time and treatment. In separate analyses, we will compare changes in quality-of-life between the two groups over time using a similar mixed-model approach. The mixed-model analysis will allow us to nest patients by site. Any baseline characteristics found to be significantly different between bCBT and EUC will be included in the model, *as will any differences in mental health service use*. The four time points (baseline, 4-, 8-, and 12-month) will allow us to assess the immediate impact of treatment and the longer-term retention, improvement, or decay in outcomes. The treatment effect will measure differences between the intervention and control groups at baseline, and the time effect will measure whether there was an overall change over time in the outcome. The term of most interest will be the interaction between time and treatment, which will indicate whether there is a difference over time between the two groups. The use of the random-coefficient model will allow us to fit a line for each participant using his/her available data, including participants with missing values, and maximize the power to detect differences.

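### The documents disagree on whether there is one primary outcome or two and give no success rule, so the type I error of the primary claim is not fixed at .05.

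*Protocol*

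**What the plan says.** **Two primary outcomes.** Protocol 3.0 puts both into one hypothesis: "The primary hypothesis is that anxiety outcomes, as measured by the GAD-7, and quality of life, measured by the SF-12". It expects bCBT to do better than EUC on them at all three follow-up visits and names none of these as the primary visit. The SAP, under its primary aim, says "We will examine the normality of the distributions of both primary outcomes", and Protocol 5.6 uses the same words.

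**One primary outcome.** Protocol 5.1 says: "The primary outcome, anxiety symptoms, will be evaluated at 4-, 8- and 12-month follow-ups". Quality of life is not mentioned there.

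**The SF-12V score.** Protocol 5.5 notes that "SF-12V responses can be summarized in component scores for physical (PCS) and mental (MCS) functioning". Neither score is called primary. The sample-size part of Protocol 5.6 uses MCS, while the analysis text in Protocol 5.6 and the SAP refers only to quality of life.

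**The tests.** The SAP gives each outcome its own model: "In separate analyses, we will compare changes in quality-of-life between the two groups over time using a similar mixed-model approach". Within a model, "The term of most interest will be the interaction between time and treatment".

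**The significance level.** It appears only in the sample-size part of Protocol 5.6. GAD-7 is sized "using a two-sided t-test with 80% power at the .05 significance level, adjusted for repeated measures", and MCS is sized separately, also two-sided at .05 with 80% power. The text supplied contains no alpha split, testing order, gatekeeping or co-primary rule.

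**The concern.** Suppose GAD-7 shows no difference and MCS is significant at .05. A reader holding Protocol 5.1 would call the trial negative. A reader holding Protocol 3.0 and the SAP could call it positive on one of two primary outcomes. A third, taking the conjunction in Protocol 3.0 literally, would say both were needed. All three could cite the plan.

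The first and third readings keep the false-positive rate at or below the level used for sizing. The second does not. The unspecified SF-12V score adds a further choice that could be made after seeing the data. The protocol abstract says positive results would support expansion of evidence-based psychotherapies in VA primary care, so what counts as positive should be settled beforehand.

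**Working it through.** **1. The plan's own figures.** The documents state no overall error rate, so there is none to reproduce. The .05 level enters through two sample-size statements.

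- GAD-7, with d = 0.38, T = 3, rho = 0.7 and 80% power: 2(1.960 + 0.842)² × (1 + 2 × 0.7) / (0.38² × 3) = 86.97, so 87 per group. The protocol states 69. One-sided .05 gives 2(1.645 + 0.842)² × 2.4 / 0.4332 = 68.5, so 69.
- MCS, with a difference of 7 and SD 11: 7/11 = 0.64, and a two-sided t-test with 40 per group has 80.3% power, as stated. The quoted effect size of 0.3 would need 175 per group.

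Both discrepancies are separate sizing matters. They do not affect the error rates below, which depend only on the level of each test and on how many tests count.

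**2. Inputs for the error rate.** The level is two-sided .05 per test (Protocol 5.6), with one interaction test per outcome (SAP). The between-outcome correlation is not in the documents, so it is varied from 0 to 0.8. For correlated tests, each statistic was treated as a single standard normal and the chance that any exceeds 1.96 in absolute value was simulated (2 million draws) under no effect on any outcome.

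**3. Results by reading.**

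| What counts as success | Correlation 0 | 0.5 | 0.8 |
|---|---|---|---|
| GAD-7 alone, one test | 5% | 5% | 5% |
| Either GAD-7 or one SF-12V score | 9.75% | 9.1% | 7.8% |
| Any of GAD-7, MCS, PCS | 14.3% | 12.5% | 9.8% |
| Both GAD-7 and one SF-12V score | 0.25% | 0.9% | not run |

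The independent cases follow directly: 1 − 0.95² = 0.0975, 1 − 0.95³ = 0.1426 and 0.05² = 0.0025. If both outcomes are required and one truly improves, the error rises to at most 5%.

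**4. Direction.** The rates count a false result in either direction. Counting only those favouring bCBT, the nominal 2.5% becomes 4.5-4.9% for two outcomes and 6.3-7.3% for three (correlation 0.5 to 0), so the relative inflation is much the same.

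**The case against.** The strongest reply is that the plan can be read without any inflation. Protocol 5.1 names anxiety alone, and the SAP singles out one interaction term per outcome, which gives 5%. Read as a strict conjunction, Protocol 3.0 is conservative. Both readings are available, so it would be wrong to say that the plan has an inflated error rate as a matter of fact. What remains is that the plan does not choose between them, and its repeated reference to two primary outcomes leaves the either-outcome reading open.

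It is also fair to say that PCS has weak support as a primary score, since only MCS is sized. The 10-14% range applies only if PCS is allowed to count.

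A reader might infer something stronger: that the three visits in the hypothesis are each tested at .05, giving six or nine primary tests. With the protocol's rho of 0.7 between visits and a between-outcome correlation of 0 to 0.7, that would give about 18-21% for two scores and 23-29% for three. The documents do not support this as the plan's rule. No section says each visit is tested at .05, the three follow-ups enter one model per outcome, and the interaction is the named test. The wording of Protocol 3.0 invites visit-level claims, which is a reason to rule them out explicitly, but those figures do not describe the plan as written.

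**Conclusion.** The point holds as a conflict between sections and a missing decision rule. The number of primary outcomes, the SF-12V score that counts and the condition for success are not settled, so the error rate of the primary claim is undefined. It is 5% or less if anxiety alone or both outcomes are required, about 8-10% if either of two interaction tests suffices, and about 10-14% if PCS counts too.

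The lower end of each range rests on the assumed between-outcome correlation and the single-normal approximation for each test. The upper ends need only independence and a .05 level per test. Rates above these would require separate tests at each visit, which the plan does not state.

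**What to change.** In Protocol 3.0, Protocol 5.6 and the SAP's primary aim, name GAD-7 as the single primary outcome, in line with Protocol 5.1. Specify one between-arm test for it at two-sided .05. The SAP's time-by-treatment interaction can fill that role if its form is written down, so this change does not require a different contrast. State that SF-12V MCS is tested at .05 only if GAD-7 is significant, and that PCS and single-visit contrasts are supportive. Make the change before any unblinded analysis.

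The cost is wording in two documents and no added patients. The downside is that no stand-alone confirmatory quality-of-life claim can be made if GAD-7 fails. If that claim matters to the sponsor, splitting alpha is a valid alternative but costs more: on the Step 1 formula, .025 per outcome needs 2(2.241 + 0.842)² × 2.4 / 0.4332 = 105.3, so 106 per group, against 87 at .05.
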